## **14                    Efficacy Analyses**

### **14.1                Primary Endpoint: ARR**

#### **14.1.1            Primary Objective: Analysis of the ARR**

Analysis (Analysis Population)	Derivation	Statistical Analysis Methods	Missing Data Handling
Primary endpoint: ARR over 24 Months			
Primary (FAS)	
ARR over 24 months. The ARR over 24 months of a patient is calculated as the number of relapses of the patient, divided by the number of days on study for that patient and multiplied by 365.25. This variable will be considered to get population estimates.
 
A relapse will be defined as per routine clinical practice, as determined by the Investigator.
 
Time on study (days) = (Date of study completion or date of study discontinuation - date of first dose of cladribine tablets + 1)
	
The population estimate will be based on the average of the ARR values for the patients in the study. The corresponding 95% CI will be reported. The Statistical Analysis System (SAS)® MEANS procedure will be used to compute these quantities. The following descriptive statistics will be reported: mean, SD, min, max, median, first quartile (Q1), and third quartile (Q3).
	
Patients discontinuing early are analyzed according to the number of years of follow-up on treatment and the number of relapses observed up to the time of discontinuation.

Secondary (PP)			

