Sensitivity (FAS)	
Model-based ARR, defined as expectation of relapses divided by time on study.
	
The estimate of the expected ARR at Month 24 will be based on a negative binomial (NB) model for relapse count, with offset equal to the log of years on study and adjustment for categorical number of relapses in the last 2 years, or since MS diagnosis if diagnosis <24 months (<math>\leq 1</math> relapse, <math>>1</math> relapse). NB regression will be computed with the SAS® Generalized Linear Model (GENMOD) procedure, using the dist=NB option in the MODEL statement.
 
*The estimate of the expected ARR at Month 24 will be based on a zero-inflated NB model for relapse count, with the offset equal to the log of years on study and adjustment for categorical number of relapses in the last 2 years, or since MS diagnosis if diagnosis <24 months (<math>\leq 1</math> relapse, <math>>1</math> relapse). NB regression will be computed with the SAS® GENMOD procedure, using the dist=ZINB option in the MODEL statement.
	
Same handling as for the primary analysis.

Analysis (Analysis Population)	Derivation	Statistical Analysis Methods	Missing Data Handling
Sensitivity (FAS)	
ARR over 24 months considering all reported relapse data. For a patient, such ARR is calculated as the total number of reported relapses in the 24 months after treatment divided by the days on study corresponding to relapse information and multiplied by 365.25.
 
Time on study with relapse information (days) = it is the time on study bounded by 366.25 for patients with relapse information only for the first year; it is the time on study bounded by 731.5 for patients with relapse information in the first year and in the second year.
	
The population estimate will be based on the average of ARR values for the patients in the study. The corresponding 95% CI will be reported. The Statistical Analysis System (SAS)® MEANS procedure will be used to compute these quantities. The following descriptive statistics will be reported: mean, SD, min, max, median, first quartile (Q1), and third quartile (Q3).
	
Patients discontinuing early are analyzed according to number of years of follow-up on treatment and number of relapses observed up to the time of discontinuation.

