Sensitivity (FAS)	
Model-based ARR, defined as expectation of reported relapses divided by time on study with relapse information.
	
The estimate of the expected ARR at Month 24 using the definition considering all the reported relapse data will be based on NB model for relapse count using the total number of reported relapses in the 24 months after treatment, with the offset equal to the log of years on study with relapse information and adjustment for categorical number of relapses in the last 2 years, or since MS diagnosis if diagnosis <24 months (<math>\leq 1</math> relapse, <math>>1</math> relapse).
 
NB regression will be computed with the SAS® GENMOD procedure, using the dist=NB option in the MODEL statement.
	
Patients discontinuing early are analyzed according to the number of years of follow-up on treatment and the number of relapses observed up to the time of discontinuation.

ARR: annualized relapse rate; CI: confidence interval; FAS: Full Analysis Set; GENMOD: generalized linear model; NB: negative binomial; PP: per protocol; SAS: Statistical Analysis System; SD: standard deviation.

\* The sensitivity analysis with the zero-inflated binomial model will be considered only if the number of patients without relapses is greater than 5%. Goodness of fit: Standardized deviance residuals will be plotted against the linear predictor to assess the goodness of fit of the model.

The primary endpoint is derived from the number of relapses collected through the eCRF forms “MS Relapse Report” and “MS Relapse Report Details.” A patient will have 0 relapses (at Visit 3 and/or Visit 6) if they reply “No” to the leading question, “Has patient experienced a new MS relapse since last scheduled or unscheduled visit? (Yes, No).” For patient replies of “Yes,” the

number of relapses will be derived from the records in the “MS Relapse Report Details” form. If at Visit 3, the answer to the leading question is not collected, the number of relapses in the first year and the total number of relapses during the second year will be missing. If at Visit 6, the answer to the leading question is not collected, the number of relapses during the second year will be missing.

For ongoing patients during the study, the time on study will take into account the patient’s last available date. This will be used in the interim analyses for all ARR evaluations (primary objective, sensitivity analyses, and secondary analyses).

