#### **14.1.4 Subgroup Analyses of ARR**

The subgroup analyses of the primary endpoint (at Month 24 for the ARR during the follow-up period) will be conducted on the FAS population.

A subgroup analysis at Month 24 of the ARR during the follow-up period for patients completing the study and patients who drop out will be performed. Estimates and CIs for the 2 subgroups will be reported using the same method as the primary analysis. This analysis will be repeated

considering the ARR based on all reported relapses, as described in the sensitivity analysis of the primary endpoint.

The same analysis will be performed for patients who complete treatment and for patients who do not complete treatment (i.e., completing Year 1 treatment but not Year 2 treatment) when the number of patients in the last group is greater than 10. This analysis will be repeated considering the ARR based on all the reported relapses, as described in the sensitivity analysis of the primary endpoint.

A subgroup analysis at Month 24 of the ARR during the follow-up period will be performed with reference to the type of MS at screening (RRMS, aSPMS, PPMS, and CIS). This analysis will be repeated considering the ARR based on all the reported relapses, as described in the sensitivity analysis of the primary endpoint.

For the primary outcome, the patterns of missingness will be explored. When the number of missing values is substantial (>5%), multiple imputation methodology will be considered for the analysis of the primary objective. At least 20 imputed datasets will be considered. The ARR at Month 24 for a patient will be considered missing if, for that patient, the number of relapses at Month 24 is missing or if the time on study for that patient is missing.

At least the following variables will be considered in the imputation model:

- ARR at Month 24
- Type of MS at screening
- Number of relapses in the previous 2 years
- Age
- Sex
- Baseline body mass index (BMI)
- Compliance

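### The SAP gives conflicting rules for early leavers without a Visit 6 answer in the primary ARR, and does not settle whether their recorded Year 1 relapses count

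*SAP*

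**What the plan says.** **Rule 1: SAP 14.1.1 table, primary FAS row.** Early leavers are "analyzed according to the number of years of follow-up on treatment and the number of relapses observed up to the time of discontinuation". The denominator runs from first dose to study completion or discontinuation. The estimate is the mean of the per-patient rates.

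**Rule 2: SAP 14.1.1, text below the table.** The primary count comes from a leading question at Visits 3 and 6. "If at Visit 6, the answer to the leading question is not collected, the number of relapses during the second year will be missing". If the Visit 3 answer is absent, "the number of relapses in the first year and the total number of relapses during the second year will be missing", with no exception for a patient who answered at Visit 6.

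**Rule 3: SAP 14.1.4.** A patient's Month 24 ARR "will be considered missing if, for that patient, the number of relapses at Month 24 is missing". The default in SAP 9 is that missing data are not replaced.

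**Dependent analyses.** The first negative binomial (NB) and zero-inflated models carry the entry "Same handling as for the primary analysis". For completers against drop-outs, "Estimates and CIs for the 2 subgroups will be reported using the same method as the primary analysis".

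**Imputation (SAP 14.1.4; Protocol 9.7.2).** "When the number of missing values is substantial (>5%), multiple imputation methodology will be considered for the analysis of the primary objective". The model is introduced by "At least the following variables will be considered in the imputation model". The list has pre-study relapses but no on-study Year 1 relapse count.

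**When relapses are recorded.** Protocol 9.1.1 limits relapse counts to Months 12 and 24. Footnote i to Table 1 in Protocol 9.2.4 has them recorded continuously, and Protocol 9.3 collects onset dates.

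**The concern.** Take a patient who answers at Visit 3, reports relapses, leaves during Year 2 and never reaches Visit 6. Rule 1 gives that patient an ARR. Rules 2 and 3 appear to give none. A programmer cannot satisfy both.

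The primary objective is to estimate this one number. If only patients with both visit answers contribute, the estimate is no longer a full-analysis-set estimate. It errs in the favourable direction if patients who relapse, or are at higher risk, leave more often. The primary-method drop-out subgroup would then have values only for drop-outs who happen to have both answers.

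The denominator is also open. Rule 1 counts time to exit, but if relapses are known only to Month 12, the months from then to exit add time without relapse information.

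**Working it through.** The visible text gives no planned ARR, sample size or exit rate, so there is no figure of the plan's to reproduce. The check compares the rules on single patients and then under assumed exit patterns.

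**1. One patient, three answers** (formulas from SAP 14.1.1)
- One Year 1 relapse, Visit 3 answered, exit on Day 540, no Visit 6. Rule 1: 1/540 × 365.25 = 0.676. Rules 2 and 3: missing. All-reported sensitivity definition, time capped at 366.25 days: 1/366.25 × 365.25 = 0.997.
- One relapse, exit on Day 250 before Visit 3. Rule 1: 1/250 × 365.25 = 1.461. Rules 2 and 3: missing.

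**2. Which rule is meant?** SAP 14.1.2 introduces the use of Year 1 relapses when Year 2 is missing as an additional sensitivity definition. That would be largely redundant for Year 2 leavers if the primary already did it. This supports reading the Month 24 count as the two-year total, but it is an inference.

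**3. Exit unrelated to relapse** (assumed: 15% leave, evenly over Months 12–24)
- Requiring both answers is unbiased, but discards 0.15/(0.15 + 2 × 0.85) = 8.1% of visit-recorded relapses.
- Time to exit with relapse information only to Month 12 is too low by 0.15 × (1 − ln 2) = 4.6%.

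**4. Exit depends on a Year 1 relapse** (assumed: gamma-Poisson relapses, true ARR 0.2, k = 0.7; exit in Year 2 of 15% without and 40% with a Year 1 relapse)
- P(no Year 1 relapse) = (1 + 0.2/0.7)^−0.7 = 0.839. Mean rate given none = 0.7/(0.7/0.2 + 1) = 0.1556. Product = 0.1305.
- Both-visits ARR = [0.85 × 0.1305 + 0.60 × (0.4 − 0.1305)] / [2 × (0.85 × 0.839 + 0.60 × 0.161)] = 0.168, about 16% too low (simulation: 15.6%).
- Share of visit-recorded relapses discarded = 0.40 × 0.2 / (0.2 + 0.85 × 0.1305 + 0.60 × 0.0695) = 0.080/0.353 = 22.7%.
- Across ARR 0.1–0.3, k of 0.7 or 1 and 30–40% exit after a Year 1 relapse: both-visits 8.7–16.1% too low, relapses counted to exit 1.6–3.9% too high, covered time 4.1–10.3% too high.

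**5. Higher-risk half leaves three times as often** (assumed: 15–30% exit overall, from Day 30): both-visits 5.8–16.9% too low, to exit within 0.3%, covered time 2.4–6.7% too low.

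**6. Dropout hazard rises after a relapse** (assumed: true ARR 0.20, dispersion 2, monthly dropout; covered time includes only patients who reached Visit 3)

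| Hazard after relapse | Leavers | To exit | Both visits | Covered time |
|---|---|---|---|---|
| unchanged | 11–24% | 0.20 | 0.20 | 0.20 |
| ×3 | 14% | 0.213 (+6.5%) | 0.177 (−11.5%) | 0.194 (−3%) |
| ×3 | 29% | 0.233 (+16.5%) | 0.151 (−24.5%) | 0.186 (−7%) |
| ×6 | 34% | 0.270 (+35%) | 0.103 (−48.5%) | 0.165 (−17.5%) |

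Over ARR 0.1–0.3 and further runs of the same kind, both-visits is about 10–49% too low (extreme: 0.152 against 0.3). To exit is about 7–43% too high. Covered time is about 1–20% too low (extreme: 0.241 against 0.3).

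**7. Imputing the both-visits ARR** (assumed 250 patients; predictive mean matching)
- Pattern of step 4: 7.8–15.5% too low on the listed variables, 0.9–1.6% with the Year 1 count added. Exit there depends on that very variable, so good recovery is built in.
- Pattern of step 5: 3.5–16.8% before and 3.0–12.2% after.
- Age, sex, BMI and compliance were set uninformative, and type of MS was not simulated.

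**The case against.** The strongest defence has four parts.

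**The conflict may be narrower than it looks.** The Month 24 count is undefined, and the SAP does not say whether a relapse report at an exit or unscheduled visit can stand in for Visit 6. If it can, fewer leavers are affected. Stopping cladribine alone does not create a leaver, because follow-up continues (Protocol 9.2.3). This stands as a limit on scope, but it also shows that the rule needs words.

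**The plan already keeps these relapses elsewhere.** The all-reported sensitivity analyses use Year 1 data. SAP 14.1.4 repeats both the completer/drop-out comparison and the imputation on the all-reported ARR. A reader might infer that leavers' relapses are lost from the report or that drop-outs will have no estimate. The documents do not support that. What remains is that a sensitivity analysis cannot settle which number is primary.

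**The imputation is more developed than a bare intention.** The SAP specifies at least 20 datasets, fully conditional specification and predictive mean matching. Its variable list is a minimum, and the SAS code it cites is not visible. It would go too far to say that the programmed model leaves out Year 1 relapses. Only the minimum list does, and the decision to impute is still open.

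**Counting to exit is no cure-all.** Under step 6 it can be further from the truth than the covered-time analysis already planned. This stands, and it shapes the fix.

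**Conclusion.** The conflict holds for early leavers with no Visit 6 answer, and for patients with a Visit 6 answer but no Visit 3 answer. Confidence is high that the stated rules disagree. That the missing rule governs the primary rests on the inference from SAP 14.1.2. This should be fixed before outcome data are examined, because choosing the rule afterwards would weaken pre-specification.

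A reader might infer that the reported ARR will be biased low. The documents do not show that: they give no exit rates and no link between exit and relapse. If exit is unrelated to relapse, the rules agree on average, provided relapses are recorded over the whole denominator period. If relapsing or higher-risk patients leave more often, the both-visits rule without imputation is too low: about 6–17% under steps 4 and 5, and 10–49% under step 6. Counting to exit ranges from about unbiased to about 43% too high, assuming relapses up to exit are fully recorded. Covered time ranges from about 20% too low to 10% too high. Neither denominator is unbiased in every case.

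**What to change.** 1. Word the primary row and the derivation text of SAP 14.1.1 and the missing-ARR rule of SAP 14.1.4 alike, and define the Month 24 relapse count. The primary FAS ARR should use all recorded relapses of early leavers, with numerator and denominator covering the same period. Use the exit date only if dated or running-page records (Protocol 9.2.4 footnote i and 9.3) capture relapses to exit, and reconcile this with Protocol 9.1.1. Otherwise use the covered time of the all-reported definition.
2. Limit the missing rule to periods with no relapse information. Let a patient with one visit answer contribute the period it covers, and say whether an exit or unscheduled report counts.
3. State that multiple imputation will be done above 5% missing, with the on-study Year 1 relapse count in the model.
4. Keep the both-visits version as a sensitivity analysis. A single overall NB rate is an optional check.

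**Cost.** SAP rewording and one imputation variable. Averaging per-patient rates stays, but the covered-time option changes the stated primary denominator and brings the primary close to an existing sensitivity analysis. Counting to exit gives very early leavers extreme values: one relapse with exit on Day 60 is 365.25/60 = 6.1 per year, which widens the interval.

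Under informative exit the primary ARR becomes less favourable than under the both-visits rule, by an amount the documents cannot fix. In the three informative rows of step 6 it rises by 20%, 54% and 162% to exit (0.213/0.177, 0.233/0.151, 0.270/0.103), or by 10%, 23% and 60% on covered time (0.194/0.177, 0.186/0.151, 0.165/0.103). The to-exit rises include overshoot of the true rate.

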#### **14.1.2 Sensitivity Analyses of the ARR**

For the NB model, the least squares means estimates of the ARR at Month 24 and the associated CI will be reported for patients having, respectively,  $\leq 1$  relapse or  $>1$  relapse in the previous 2 years, or since MS diagnosis, if diagnosis is  $<24$  months. These quantities will be obtained using the LSMEANS statement with the ILINK option.

For the zero-inflated NB model, the following approach will be used to report the estimates of the ARR at Month 24 and associated CIs for patients having, respectively,  $\leq 1$  relapse or  $>1$  relapse in the previous 2 years, or since MS diagnosis, if diagnosis is  $<24$  months. The STORE statement in PROC GENMOD will be used to save the fitted model. Then the fitted model will be used in proc PLM with the SCORE statement and the ILINK and NOOFFSET options.

Standardized deviance residuals will be plotted against the linear predictor to assess the goodness of fit of the model (NB or zero-inflated NB). The STDRESDEV statement with the XBETA option in the GENMOD procedure will be used.

A further sensitivity analysis will be carried out considering different definitions of the ARR based on all reported relapses. Such additional definitions will derive the ARR over the 24 months using the number of available relapses over the first year even if information on the relapses in the second year is missing. The time on study for the calculation of the ARR will be bounded by the time on study with relapse information. Such logic will be used also for an additional sensitivity analysis using the NB model.

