### **Significance Level**

When CIs are to be calculated, these will be two-sided, with a confidence probability of 95%, unless otherwise specified in this IAP. For continuous data, CIs for the mean will be calculated assuming a normal distribution of the data. CIs for binary endpoints will be presented using the Clopper-Pearson method. All statistical tests mentioned in this IAP are to be regarded as exploratory. The significance level is 5% two-sided. If p-values are to be presented for descriptive purposes, it will be indicated with the statement that no inferential conclusion should be drawn from the p-value.

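### SAP 14.1.2 specifies the negative binomial relapse rates only by prior-relapse stratum, so no overall model-based ARR is specified for comparison with the primary estimate

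*SAP*

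**What the plan says.** The primary objective is a single ARR over 24 months. In SAP 14.1.1, "The population estimate will be based on the average of the ARR values for the patients in the study", with a CI. SAP section 9 states that CIs "these will be two-sided, with a confidence probability of 95"%.

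The sensitivity rows of the same table define the quantity as "Model-based ARR, defined as expectation of relapses divided by time on study", and continue in the singular: "The estimate of the expected ARR at Month 24 will be based on a negative binomial (NB) model for relapse count". The model has the log of years on study as offset and "adjustment for categorical number of relapses in the last 2 years, or since MS diagnosis if diagnosis" is under 24 months, in two categories: at most 1, or more than 1. A zero-inflated version (ZINB) has the same offset and covariate and "will be considered only if the number of patients without relapses is greater than 5"%.

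SAP 14.1.2 says what is to be reported. For NB, "the least squares means estimates of the ARR at Month 24 and the associated CI will be reported for patients having, respectively", at most 1 or more than 1 prior relapse. For ZINB, "the following approach will be used to report the estimates of the ARR at Month 24 and associated CIs for patients having, respectively", the same two groups.

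SAP 14.1.1 also plans a second NB model, on all reported relapses, with the same covariate. SAP 14.1.2 carries the relapse and time definitions over to it but does not say which estimates it will report.

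Protocol 9.7.3 describes the NB sensitivity analysis with time as the explanatory variable and mentions neither a prior-relapse covariate nor stratified output.

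**The concern.** A sensitivity analysis should estimate the same quantity as the primary analysis under different assumptions, so that the two results can be set side by side. Here the primary result is one number for the FAS, while the described count-model output is two numbers for two groups of patients.

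The comparison cannot be made within strata either. Neither subgroup list (SAP 8.2 and 14.1.4) includes prior relapses, so the primary-method ARR is not planned for those two groups. With a single arm, the covariate adjusts no treatment contrast. In the reported output it only splits the estimate.

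The check lost is a relevant one. The primary estimator divides each patient's count by that patient's own time on study and weights all patients equally, so a relapse in a short follow-up can count heavily. A count model with a log-time offset handles exposure differently and would show whether this matters.

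**Working it through.** **1. Which planned results are overall, and which use a count model**

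| Analysis (SAP) | Estimator | Overall ARR specified? |
|---|---|---|
| Primary, FAS (14.1.1) | mean of patient ARRs | yes |
| All reported relapses (14.1.1, 14.1.2) | mean of patient ARRs | yes |
| PP (14.1.3) | mean of patient ARRs | yes, unless omitted because PP is at least 90% of FAS (8.2) |
| Multiple imputation (14.1.4) | patient ARRs, imputed where missing | yes, considered if over 5% missing |
| NB (14.1.2) | count model | no, two strata |
| ZINB (14.1.2) | count model | no, two strata |
| NB, all reported relapses (14.1.1) | count model | output not specified |

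No row combines a count model with an overall ARR.

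**2. Can a stratum value stand in for the overall ARR?**

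The readable text gives no stratum rates, shares or sample size (the precision table is redacted), so the inputs here are assumptions. With w the share of patients having at most 1 prior relapse:

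overall ARR = w × ARR(≤1) + (1 − w) × ARR(>1)

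For assumed stratum ARRs of 0.14 and 0.35:
- w = 0.8: 0.112 + 0.070 = 0.182
- w = 0.7: 0.098 + 0.105 = 0.203
- w = 0.6: 0.084 + 0.140 = 0.224

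Other assumed rates, by share with more than 1 prior relapse:

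| ARR(≤1), ARR(>1) | 10% | 20% | 30% | 50% |
|---|---|---|---|---|
| 0.10, 0.20 | 0.11 | 0.12 | 0.13 | 0.15 |
| 0.10, 0.30 | 0.12 | 0.14 | 0.16 | 0.20 |
| 0.15, 0.25 | 0.16 | 0.17 | 0.18 | 0.20 |

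The overall value moves with the patient mix and equals neither stratum value.

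**3. Why the averaging must be on the rate scale**

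The SAP plans no average of the two LS means. If one were added on the log scale and back-transformed, it would miss the target. Equal weights give √(0.14 × 0.35) = 0.221 whatever the mix. Observed weights at w = 0.7 give exp(0.7 ln 0.14 + 0.3 ln 0.35) = 0.184, against 0.203 on the rate scale.

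**4. Does an overall model ARR match the primary target?**

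Simulation, 400 runs per N. Assumptions: 25% with more than 1 prior relapse, true ARRs 0.10 and 0.30 (overall 0.75 × 0.10 + 0.25 × 0.30 = 0.15), NB dispersion 1, about 15% leaving early for reasons unrelated to relapse. Medians over the usable fits (389 and 399), with median SE in brackets:

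| | N = 150 | N = 250 |
|---|---|---|
| NB, ≤1 stratum | 0.0990 | 0.0993 |
| NB, >1 stratum | 0.2880 | 0.2972 |
| NB, standardised to observed mix | 0.1465 (0.0265) | 0.1468 (0.0209) |
| NB, offset only | 0.1463 | 0.1466 |
| Mean of patient ARRs | 0.1465 (0.0280) | 0.1464 (0.0220) |

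Either overall NB figure is directly comparable with the primary-type mean. The stratum figures are not.

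**5. Where the estimators can part**

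A patient with 1 relapse in 90 days has an ARR of 365.25/90 = 4.06. With an assumed N = 200, this adds 4.06/200 = 0.020 to the mean of patient ARRs. In a pooled rate over about 200 × 2 = 400 person-years, the same relapse adds 1/400 = 0.0025. This applies only if the patient's count enters the analysis; SAP 14.1.1 sets the count to missing when the relapse question is not collected at Visit 3 or Visit 6.

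**The case against.** A reader might infer that the sensitivity analyses cannot confirm or contradict the primary result, or that an overall model-based ARR is ruled out. The documents do not support either reading.

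- Three other analyses give an overall ARR: all reported relapses, PP and multiple imputation (the last two conditionally). They test the handling of missing relapse data, the analysis population and the imputation. What they do not test is the estimator, which they share with the primary analysis.
- SAP 14.1.1 speaks of one expected ARR, and 14.1.2 does not say that the stratum estimates are the only output. Table shells are not available for this review and may contain an overall row. This stands: the defect is a mismatch between the two sections, not a decision to leave the overall value out.
- The stratum values bracket the overall one, so a primary ARR outside both would signal conflict. An overall point estimate could also be worked out from the stratum counts. Both are true. But a primary ARR between the two values settles little, no CI would come with the hand calculation, and SAP 11.3 plans prior relapses as a continuous variable without naming the split at 1.
- The practical gain may be small. In the simulation the overall NB figure and the primary-type mean agree to within 0.001. That run assumed early leaving unrelated to relapse; where that fails, as the example in step 5 suggests, the comparison would be informative.

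**Conclusion.** The point holds as a gap in the specified output. SAP 14.1.2 specifies the NB and ZINB estimates by prior-relapse stratum and no overall model-based ARR, although SAP 14.1.1 refers to a single expected ARR. For the all-reported-relapses NB model the output is not specified at all. As written, the count models provide no like-for-like check of the mean-of-patient-ARRs estimator, overall or by stratum.

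The size cannot be stated from the documents. Under the assumed stratum rates of 0.14 and 0.35, the overall ARR ranges from 0.18 to 0.22 as the lower stratum's share falls from 80% to 60%. This shows only that a stratum estimate is no substitute; it is not an estimate of bias. The primary estimate and its CI are unaffected. The change is worth making before the final analysis, because SAP section 4 requires analyses not identified in the plan to be flagged as such in the study report.

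**What to change.** In SAP 14.1.2, for each of the three models (NB, ZINB where fitted, and the all-reported-relapses NB), add one overall ARR with 95% CI. Compute it as the average, over all FAS patients in the model, of the predicted one-year rate on the response scale. For ZINB the prediction must include the zero-inflation probability: (1 − probability of a structural zero) × the NB mean. Take the CI by the delta method or bootstrap.

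For the NB models, a model with the offset only is an acceptable alternative and is close to protocol 9.7.3. It does not cover the ZINB model.

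Keep the two stratum estimates as supportive output, state the output for the all-reported-relapses NB model, and align the wording of 14.1.1 and 14.1.2. No new data are needed. The cost is a few lines of code and one table row per model.
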